6.3 RESPONSE CRITERIA

6.3.1 Response Assessments

Tumor response will be assessed radiographically after cycle 2 and 4 treatments are completed by the investigator using the Immune-Modified Response Evaluation Criteria In Solid Tumors, i.e., imRECIST criteria [\[88\]](#) for Immune-related Best Overall Response (irBOR, Section **6.4.1**) will be derived based on reported lesion responses at different evaluation time points from the first trial treatment administration until immune-related disease progression per imRECIST [\[88\]](#) according to the following rules:

- irCR = at least two radiographic determinations of CR at least 4 weeks apart and before irPD
- irPR = at least two radiographic determinations of PR or better at least 4 weeks apart and before irPD (and not qualifying for an irCR)
- irSD = at least one radiographic assessment of SD (or better) ≥ 6 weeks after the first trial treatment administration and before irPD (and not qualifying for irCR or irPR).
- irPD = at least two consecutive radiographic determinations of PD at least 4 weeks apart.

Only tumor assessments performed before the start of any further anti-cancer treatment will be considered in the assessment of irBOR.

Immune-related Objective Response (irOR) is defined as irCR or irPR according to irRECIST from the first trial treatment administration until irPD or death due to any cause. Both irCR and irPR must be confirmed by repeat assessments performed no less than 4 weeks after the criteria for immune-related response are first met. Also, irPD must be confirmed by a second, consecutive assessment at least 4 weeks apart. Immune-related OR rate (irORR) is the proportion of subjects with irOR in the analysis set.

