Target lesions: All measurable lesions up to a maximum of 2 lesions per organ and 5 lesions in total, representative of all involved organs, should be identified as **target lesions** and recorded and measured at baseline. Target lesions should be selected on the basis of their size (lesions with the longest diameter), be representative of all involved organs, but in addition should be those that lend themselves to reproducible repeated measurements. It may be the case that, on occasion, the largest lesion does not lend itself to reproducible measurement in which circumstance the next largest lesion which can be measured reproducibly should be selected. A sum of the diameters (longest for non-nodal lesions, short axis for nodal lesions) for all target lesions will be calculated and reported as the baseline sum diameters. If lymph nodes are to be included in the sum, then only the short axis is added into the sum. The baseline sum diameters will be used as reference to further characterize any objective tumor regression in the measurable dimension of the disease.

Non-target lesions: All other lesions (or sites of disease) including any measurable lesions over and above the 5 target lesions should be identified as **non-target lesions** and should also be recorded at baseline. Measurements of these lesions are not required, but the presence, absence, or in rare cases unequivocal progression of each should be noted throughout follow-up.

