6.3.5 Evaluation of Target Lesions

Complete Response (CR): Disappearance of all target lesions. Any pathological lymph nodes (whether target or non-target) must have reduction in short axis to <10 mm.

Partial Response (PR): At least a 30% decrease in the sum of the diameters of target lesions, taking as reference the baseline sum diameters.

Progressive Disease (PD): At least a 20% increase in the sum of the diameters of target lesions, taking as reference the smallest sum on study (this includes the baseline sum if that is the smallest on study). In addition to the relative increase of 20%, the sum must also demonstrate an absolute increase of at least 5 mm. (Note: the appearance of one or more new lesions is also considered progressions).

Stable Disease (SD): Neither sufficient shrinkage to qualify for PR nor sufficient increase to qualify for PD, taking as reference the smallest sum diameters while on study.

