10 STATISTICAL CONSIDERATIONS

10.1 STATISTICAL HYPOTHESES

10.1.1 Primary Endpoints

Overall Response (CR + PR) by irRECIST 1.1 criteria in patients who receive at least 1 cycle of therapy with the 4 mcg/kg dose of rhIL-15.

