10.3.2 Evaluable for objective response

Only those patients who have measurable disease present at baseline and have received at least one cycle of therapy with 4mcg/kg dose of rhIL-15, will be assessed on an intent to treat basis. Patients who discontinue treatment or die and are not restaged will be considered to be non-responders and included in calculating the response rate. Patients will have their response classified according to the definitions stated above, Section **6.3**. (NOTE: Patients who exhibit objective disease progression prior to the end of Cycle 1 will also be considered evaluable).

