16.5 APPENDIX E: MODIFIED IMMUNE-RELATED RESPONSE CRITERIA (irRECIST)

This new classification is based on the recent learning from clinical studies with cancer immunotherapies that even if some new lesions appear at the beginning of a treatment or if the total tumor burden does not increase substantially, tumor regressions or stabilizations might still occur later. The irRC were created using bi-dimensional measurements (as previously widely used in the World Health Organization criteria). For this trial, the concepts of the irRC are combined with RECIST 1.1 to come up with the modified irRC.

For modified irRC, only target and measurable lesions are taken into account. In contrast to the RECIST 1.1 criteria, the modified irRC criteria (a) require confirmation of both progression and response by imaging at 6-8 weeks after initial imaging and (b) do not necessarily score the appearance of new lesions as progressive disease if the sum of lesion diameters of target lesions (minimum of 10 mm per lesion, maximum of 5 target lesions, maximum of 2 per organ) and measurable new lesions does not increase by $\geq 20\%$.

The same method of assessment and the same technique should be used to characterize each identified and reported target lesion(s) at baseline, during the trial, and at the end of trial visit. All measurements should be recorded in metric notation. The modified irRC based on RECIST 1.1 are displayed below.

Modified immune-related response criteria are defined as follows:

New measurable lesions: Incorporated into tumor burden.

New non-measurable lesions: Do not define progression but precludes (irCR).

Overall irCR: Complete disappearance of all lesions (whether measurable or not) and no new lesions. All measurable lymph nodes also must have a reduction in short axis to 10 mm.

Overall irPR: Sum of the longest diameters of target and new measurable lesions decreases $\geq 30\%$.

Overall irSD: Sum of the longest diameters of target and new measurable lesions neither irCR, irPR, (compared to baseline) or irPD (compared to nadir).

Overall irPD: Sum of the longest diameters of target and new measurable lesions increases $\geq 20\%$ (compared to nadir), confirmed by a repeat, consecutive observations at least 4 weeks (normally it should be done at 6 weeks) from the date first documented.

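### The protocol names several conflicting criteria for the primary response count, and one patient classified differently can reverse either Simon decision

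*Combined protocol and SAP*

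**What the plan says.** - **Endpoint.** Section 10.1.1 gives the primary endpoint as "Overall Response (CR + PR) by irRECIST 1.1 criteria", and 10.2 repeats that label.
- **Classification.** Section 10.3.2, which defines the set evaluable for objective response, says "Patients will have their response classified according to the definitions stated above" and cites Section 6.3 as a whole.
- **Section 6.3.1.** The investigator assesses scans "using the Immune-Modified Response Evaluation Criteria In Solid Tumors, i.e., imRECIST criteria" to derive immune-related best response. Further down, the same section defines objective response as irCR or irPR by irRECIST.
- **Sections 6.3.5 to 6.3.7.** These are RECIST 1.1 rules. In 6.3.5, "the appearance of one or more new lesions is also considered progressions". The 6.3.7 table gives overall PD for any new lesion, whatever the target response, and best response is read only up to progression. Non-target progression is also PD, but 6.3.6 requires it to be unequivocal and to reflect overall disease status.
- **Section 6.4 and Appendix E.** Section 6.4 says irRECIST is also used and refers to Appendix E. Those criteria "do not necessarily score the appearance of new lesions as progressive disease". They count only target and measurable lesions, and irPR is reached when the "Sum of the longest diameters of target and new measurable lesions decreases" by at least 30%.
- **Stage 1 boundary.** Section 10.2 describes the response needed in 1 of 9 patients as a fall of more than 20% in tumor volume.

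**The concern.** No section says which of these rules decides the counts for the two Simon boundaries. The rules disagree on the case that immune criteria were written for: tumor burden falls while a new lesion appears. Section 6.3.2 expects such cases and allows treatment to continue through them.

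The boundaries leave no slack. The trial stops at 0 of 9 and continues at 1 of 9. It fails at 2 of 17 and succeeds at 3 of 17. The trial is open-label and single-arm, and the investigator assesses response. If the governing rule is open, it could be settled after the scans are known.

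**Working it through.** **1. The plan's own figures (Section 10.2).** Inputs are a null rate of 5%, a target rate of 25%, continuation with at least 1 response in 9, and success with at least 3 in 17 (8 patients in stage 2). With X1 ~ Bin(9, p) and X2 ~ Bin(8, p):

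P(success) = P(X1=1)·P(X2≥2) + P(X1=2)·P(X2≥1) + P(X1≥3)

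- p = 0.05: stopping probability 0.95^9 = 63.0% (stated 63%). P(success) = 0.2985 × 0.0572 + 0.0629 × 0.3366 + 0.0084 = 4.7%.
- p = 0.25: chance of passing stage 1 is 1 − 0.75^9 = 92.5% (stated 92%). P(success) = 0.2253 × 0.6329 + 0.3003 × 0.8999 + 0.3993 = 81.2%.

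A search over two-stage designs with type I error at most 5% and power at least 80% returns this design as the optimal one. The design arithmetic is sound.

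**2. One set of scans under two rules.** Take non-nodal target lesions summing to 60 mm that shrink to 30 mm, with one new measurable lesion of 10 mm.

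- Sections 6.3.5 to 6.3.7: the targets alone fall by 50%, but the new lesion makes the overall response PD.
- Appendix E: the sum is 30 + 10 = 40 mm, and (40 − 60)/60 = −33%, so irPR if confirmed.

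One such patient moves 0/9 to 1/9, or 2/17 to 3/17.

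**3. Nodal lesions.** Section 6.3.3 sums diameters as "longest for non-nodal lesions, short axis for nodal lesions". Appendix E, read literally, sums longest diameters. For a single target node going from 30 × 20 mm to 24 × 13 mm, the long axis changes by (24 − 30)/30 = −20%, which is not a PR. The short axis changes by (13 − 20)/20 = −35%, which is. Here Appendix E is the stricter rule.

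**4. Size over an assumed range.** Let f be the share of irRECIST responders who are PD by the RECIST 1.1 rules. The documents do not give f, so the range is an assumption. Case A: 25% is the irRECIST rate but responses are counted by RECIST 1.1, so the effective rate is 0.25 × (1 − f). Case B: 5% is a RECIST 1.1 rate but responses are counted by irRECIST, so the effective null is 0.05/(1 − f). Each rate goes into the formula of step 1.

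| f | A: rate | A: pass stage 1 | A: power | B: null rate | B: type I error |
|---|---|---|---|---|---|
| 0 | 25% | 92.5% | 81.2% | 5.0% | 4.7% |
| 10% | 22.5% | 89.9% | 74.5% | 5.6% | 6.0% |
| 20% | 20% | 86.6% | 66.3% | 6.3% | 8.0% |
| 30% | 17.5% | 82.3% | 56.6% | 7.1% | 10.9% |
| 40% | 15% | 76.8% | 45.6% | 8.3% | 15.3% |

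The opposite mismatch also exists. If 5% is the irRECIST rate and counting is by RECIST 1.1, type I error falls to between 3.6% (f = 10%) and 1.2% (f = 40%).

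**The case against.** The best defense is that the pointer in 10.3.2 can be met inside Section 6.3 without touching RECIST 1.1. Section 6.3.1 defines immune-related objective response by irRECIST and the response rate as the proportion with it, which agrees with 10.1.1 and 10.2. Section 6.3.2 allows treatment past RECIST progression, and 6.3.3 is headed as RECIST parameters, so 6.3.3 to 6.3.7 could be read as background. This stands to the extent that a reader who infers that 10.3.2 sends the primary count to RECIST 1.1 alone goes too far. It does not settle the matter, because no text gives 6.3.1 precedence, 6.3.1 itself mixes imRECIST with irRECIST, and the stage 1 sentence in 10.2 matches neither.

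The contrast also has limits, and these stand. Section 6.3.6 says non-target progression should not normally override target status. Under Appendix E, new measurable lesions enter the sum and can prevent irPR or cause irPD, and irCR allows no new lesion. Progression after a confirmed response leaves best response unchanged under either system.

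A reader might also infer that Appendix E is simply the looser rule and inflates the false-positive rate, for example to 14.0% or 22.3% if the null rate became 8% or 10%. The arithmetic is right, but nothing in the documents supports those shifts. The protocol does not say that its 5% is a RECIST 1.1 rate, the nodal example runs the other way, and 6.3.2 places the gain from immune criteria mostly in disease control and PFS.

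**Conclusion.** The concern holds as a contradiction about which criterion governs the primary count. The documents do not support a claim that the count will differ, or that it is biased in one direction. It can differ when a new lesion or unequivocal non-target progression appears by the time of the response or its confirming scan, or when nodal targets are measured on different axes. One such patient is enough to reverse either Simon decision.

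The effect on operating characteristics is conditional. For an assumed discordance of 10 to 40%, either power drops from 81.2% to 74.5 to 45.6% or type I error rises from 4.7% to 6.0 to 15.3%, depending on which criterion the 25% and 5% rates refer to. With no discordance both stay as planned. The text needs correction whatever the true discordance, because the primary verdict cannot be reproduced from the protocol as written.

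**What to change.** 1. In 10.1.1, 10.2, 10.3.2 and 6.3.1, name one criterion, by section or appendix, for both Simon decisions. Appendix E is the natural choice because 10.1.1 and 10.2 already name irRECIST.
2. Rewrite the stage 1 sentences in 10.2 on that criterion, removing the 20% tumor-volume wording, and remove the competing imRECIST reference in 6.3.1.
3. State in 10.2 that the 5% null rate is on the chosen criterion.
4. Label 6.3.5 to 6.3.7 as RECIST 1.1 and report that response rate as a sensitivity analysis.
5. Reconcile Appendix E with 6.3.3 on the nodal axis.
6. Reconcile the confirmation interval: Appendix E gives 6 to 8 weeks, 6.3.1 at least 4 weeks, and the Appendix F calendar a confirmatory scan 4 weeks after first response. Naming Appendix E without this step would leave the calendar out of line with the endpoint.

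The cost is protocol wording and one extra tabulation from the same lesion measurements, provided both nodal axes are recorded. No extra scans are implied if the reconciled interval fits the existing calendar.

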10.3.3 Evaluable for Non-Target Disease Response

Patients who have lesions present at baseline that are evaluable but do not meet the definitions of measurable disease and have received at least one cycle of therapy will be assessed on an intent to treat basis. Patients who discontinue treatment or die and are not restaged will be considered to be non-responders. The response assessment is based on the presence, absence, or unequivocal progression of the lesions.

10.4 STATISTICAL ANALYSES

10.4.1 General Approach

The response rate will be determined and reported along with a 95% confidence interval using the Agresti-Coull method [90]. Other time-to-event outcomes will be reported using Kaplan-Meier curves.

10.4.2 Analysis of Secondary Endpoints

Secondary clinical endpoints of the rate and severity of AEs will be summarized by grade and type of toxicity. The progression-free survival (PFS) and overall survival (OS) will be calculated from the on-study date using the Kaplan Meier method. For PFS and OS, censoring time is defined as time from baseline to date of last follow-up. Duration of response for responders also calculated using the Kaplan-Meier approach is defined as time from the initial response to progression or death, whichever occurs first. Censoring time for duration of response is defined as time from the initial response to date of last follow-up.

The secondary objectives include characterization of biological effects of this treatment and determination of effects of IL-15 on the ADCC capacity of ex vivo PBMCs. These exploratory analyses will be summarized.

11 COLLABORATIVE AGREEMENTS

11.1 COOPERATIVE RESEARCH AND DEVELOPMENT AGREEMENT (CRADA) - EMD SERONO

This study will be incorporated into an existing CRADA (#02666) between the National Cancer Institute and EMD Serono, the manufacturer of avelumab.

12 HUMAN SUBJECTS PROTECTIONS

12.1 RATIONALE FOR SUBJECT SELECTION

All subjects from both sexes and all racial/ethnic groups are eligible for this study if they meet the eligibility criteria outlined in the protocol and provide informed consent to protocol participation. Pregnant or nursing mothers are excluded because of the potential teratogenic effects of therapy.

There have been no studies of IL-15 in patients with HIV on or off ART. Two non-human primates with SIV who were not on ART and received rhIL-15 on Study 2078-10804 both died, while subsequent animals who received viral suppression were seemingly unaffected. rhIL-15 may therefore contribute to morbidity/mortality in patients with a detectable viral load. Since potential toxicity of IL-15 and avelumab may interfere with ART adherence and optimal viral suppression, patients with HIV may be exposed to additional toxicity for unknown potential benefit of IL-15 and should therefore be excluded from this study.

We expect men and women to be equally represented among the enrolled patients.

12.2 PARTICIPATION OF CHILDREN

Subjects under the age of 18 are excluded because ccRCC is rare in young patients, and the inclusion of an occasional younger patient will not provide generalizable information that would justify their inclusion on this study. Additionally, because no dosing or adverse event data are currently available on the use of rhIL-15 in combination with avelumab in patients <18 years of age, children are excluded from this study, but may be eligible for future pediatric trials.

12.3 RISK/BENEFIT ASSESSMENT

12.3.1 Known Potential Risks

The potential risks of adding rhIL-15 to avelumab include, in particular infusion reactions (including chills, fever, hypotension, headache, flushing, dizziness), fatigue, rash, Liver Function Test (LFT) abnormalities, and cytopenias.

Since fevers, rigors, lymphopenia, and LFT elevations occurred only during IL-15 infusion in the continuous IV trial, and since avelumab is not given concomitantly, these toxicities are not expected to overlap. Avelumab manufacturer recommendations for discontinuing therapy will be followed, including for grade 3-4 LFT elevations. Fatigue and rash are potential overlapping toxicities, and both will be monitored closely.

12.3.2 Risks related to Imaging

CT scans often use a contrast agent. There is a small risk of having a reaction to the contrast and most often include nausea, pain in the vein where the contrast is given, headache, metallic and/ or bitter taste in the mouth and a warm, flushing feeling. Rarely, some people have more severe allergic reactions to the contrast which may include skin rashes, shortness of breath, wheezing or low blood pressure.

12.3.3 Risks from Radiation Exposure

The procedures for performing the CT scans will follow clinical policies, no special procedures apply to these additional assessments for research purposes. In summary, subjects may receive additional radiation exposure from up to seven (7) additional CT scans of the neck, chest, abdomen, and pelvis.

The total additional radiation dose for research purposes will be approximately 9.1 rem.

12.3.4 Blood draws

Side effects of blood draws include pain and bruising, lightheadedness, and rarely, fainting.

12.3.5 MRI

People are at risk for injury from the MRI magnet if they have some kinds of metal in their body. People with fear of confined spaces may become anxious during an MRI. Those with back problems may have back pain or discomfort from lying in the scanner. The noise from the scanner is loud enough to damage hearing, especially in people who already have hearing loss.

There are no known long-term risks of MRI scans.

12.3.6 Gadolinium enhanced MRI

During part of the MRI patient may receive gadolinium, a contrast agent, through an intravenous (IV) catheter (small tube). It will be done for research purposes.

The risks of an IV catheter include bleeding, infection, or inflammation of the skin and vein with pain and swelling. Participants undergoing gadolinium enhanced MRIs may also be at risk for kidney damage.

Most of the gadolinium contrast is eliminated in the urine. However, recent studies have found very small amounts of residual gadolinium in the body, including the brain and bone, by imaging and at autopsy. Macroyclic gadolinium-containing contrast agents are substantially less likely to leave gadolinium behind than linear agents. There is presently no evidence that the retained gadolinium is associated with any adverse effects or other health risks. Participants undergoing gadolinium enhanced MRIs may also be at risk for kidney damage.

12.3.7 Tumor Biopsy (Optional)

All care will be taken to minimize risks that may be incurred by tumor sampling. However, there are procedure-related risks (such as bleeding, infection, and injury) that will be explained fully during informed consent.

12.3.8 Electrocardiogram

Some skin irritation can occur where the ECG/EKG electrodes are placed. The test is completely painless, and generally takes less than a minute to perform.

12.3.9 Central line

A non-tunneled central catheter is a soft tube a doctor puts into a vein leading to your heart. It is a way to take blood samples or give you fluids, medicines, or nutrients over a long period of time. Possible side effects include pain, bleeding, bruising, and, on rare occasions, swelling in your arm, chest, neck, or face on the same side as the catheter or infection.

12.3.10 Known Potential Benefits

The potential benefit of adding rhIL-15 to avelumab in treatment of metastatic refractory ccRCC is unknown, but single-agent ICI have shown activity as outlined in Section [1.2.4](#).

12.3.11 Assessment of Potential Risks and Benefits

An estimated 20 to 50 % of mRCC are PD-L1+ [34], and since the anti-PD-L1 antibody avelumab has shown ADCC activity *in vitro*, agents that may enhance ADCC by increasing number and activity of Fc-binding effector cells — such as rhIL15 — could improve efficacy of avelumab in these diseases. Although the clinical benefit of these drug(s) has not yet been established, the intent of offering this treatment is to provide a possible therapeutic benefit, and thus the patient will be carefully monitored for tumor response and symptom relief in addition to safety and tolerability. In addition to the tumor cells, PD-L1 is also expressed on normal immune cells. Since avelumab has potential for *in vivo* ADCC activity, immune cell subsets may change. However, when 123 different immune cell subsets were analyzed in 28 patients with solid tumors who received avelumab during a phase I trial, there were no changes at any of the time points in any of the 123 subsets tested regardless of their PD-L1 expression before and during treatment [43]. PBMC samples were obtained before Avelumab, and after 1, 3, and 9 doses of the drug. A limited number of immune cell subsets will also be tested in our trial, both in PBMCs and optional tissue biopsies.

